17.1.2 Retention of Records

An Investigator must maintain adequate records to include the disposition of the study medication(s) and adequate and accurate source documentation that record all observations and other data pertinent to the investigation on each patient in the study. These records are to include the case report forms (CRFs), source documentation, and supporting data, including, for example, signed and dated informed consent forms and medical records (including progress notes by the physician and/or other qualified medical personnel, the patient's hospital and clinic chart[s], and the nurses' notes).

The FDA (21 CFR §312.62[c]) states that the Investigator shall retain the required records:

- a. For a period of 2 years following the date a marketing application is approved for the drug for the indication for which it is being investigated; or
- b. If no application is to be filed or if the marketing application is not approved for such indication, until 2 years after the investigation is discontinued and the FDA is notified.

If neither a) nor b) applies, then the Investigator shall retain the required records for a minimum of 15 years after the completion or discontinuation of the study.

For sites outside the US, the Investigator must comply with US FDA regulations and with the record retention policies of the relevant national and local health authorities. The Investigator must obtain the Sponsor's written permission before disposing of any records.

If the Investigator retires, relocates, or for any reason withdraws from the study, then the study records may be transferred to an acceptable person or institution with the written approval of the Sponsor.

18. REPORTING STUDY RESULTS AND PUBLICATION POLICY

Following analysis of the data and upon request by the Investigator, the Sponsor will supply a listing of site-specific treatment assignments, tabulated data, and statistical analysis, as appropriate. A summary of the study results will be provided to each Investigator following its release by the Sponsor. The Investigator will acknowledge receipt of any data listings or study results.

Guidelines concerning publication of the results of this clinical study are contained within the formal Clinical Study Agreement associated with this protocol.

08 JUN 2020

20. APPENDICES

APPENDIX A SCHEDULE OF ASSESSMENTS FOR PATIENTS RANDOMIZED TO SEL-212

Assessment	Scr.		Treatment Period (TP)																EOS ¹	ET		
			TP1 ²		TP2 ²		TP3 ²				TP4 ²		TP5 ²		TP6 ²							
Day	-45 d	-7 d ³	D0	D21	D0 ⁴	D21	D0 ⁴	D7	D14	D21	D0 ⁴	D21	D0 ⁴	D21	D0 ⁴	D7	D14	D21	D28 ²⁰			
Informed Consent	X																					
Demographics	X																					
Inclusion/Exclusion	X																					
Medical History	X																					
Physical Examinations	X ⁵		X ⁶		X ⁶		X ⁶				X ⁶		X ⁶		X ⁶					X ⁵		X ⁵
Vital Signs	X	X	X ⁷		X ⁷		X ⁷				X ⁷		X ⁷		X ⁷		X	X	X			X
Weight and Height ⁸	X	X		X		X				X		X		X				X	X			X
Tophus Assessment	X																			X		X
12-Lead ECG	X																			X		X
Screening Labs ⁹	X																					
Screening Lab: Anti-PEG-Ab	X																					
Urine Pregnancy Test	X																					
Washout: ULTs		X ¹⁰	Patients will abstain from ULT use after the ULT washout period																			
Document ULTs Discontinued		X																				
Dispense Premedication: Gout Flare and Infusion Reaction		X																				
Premedication: Gout Flare		X ¹¹	Continuously																			
Premedication: Infusion Reaction			X ¹²		X ¹²		X ¹²				X ¹²		X ¹²		X ¹²							
Safety Labs: Chemistry ¹³	X		X	X		X				X		X		X					X	X		X
Safety Labs: Hematology ¹⁴	X		X	X		X				X		X		X				X	X		X	
Safety Labs: Coagulation ¹⁵	X		X	X		X				X		X		X				X	X		X	
Safety Labs: Lipids ¹⁶	X		X	X		X				X		X		X				X	X		X	
Safety Labs: Urinalysis ¹⁷	X		X	X		X				X		X		X				X	X		X	
Safety Labs: Anti-drug-Ab																			X		X	
Gout Flare Assessment	X		X	X	X	X	X	X	X	X	X	X	X	X	X	X	X	X	X	X	X	
Joint Assessment (tenderness, swelling)			X								X								X		X	

Appendix A SCHEDULE OF ASSESSMENTS FOR PATIENTS RANDOMIZED TO SEL-212, CONTINUED

Assessment	Scr.	Treatment Period (TP)																EOS ¹	ET			
		TP1 ²		TP2 ²		TP3 ²				TP4 ²		TP5 ²		TP6 ²								
Day	-45 d	-7 d ³	D0	D21	D0 ⁴	D21	D0 ⁴	D7	D14	D21	D0 ⁴	D21	D0 ⁴	D21	D0 ⁴	D7	D14	D21	D28 ²⁰			
Health Questionnaires ¹⁸			X										X							X		X
Collect Sample for SUA	X				Refer to Schedule of Assessments in Appendix B for SUA Sample Collection during Treatment Period																	X
Study Drug Administration					Refer to Schedule of Assessments in Appendix B for Study Drug Administration during the Treatment Period																	
Concomitant Medications / Procedures					Continuously																X	X
AE/SAE Collection	X ¹⁹	X ¹⁹			Continuously																X	X

1. Phone call at 30 (+ 4) days after the last study drug infusion for assessment of concomitant medications/procedures, AEs, and SAEs.
2. Visit window at Day 21 of each Treatment Period is -2 days to +1 day.
3. Visit window is -2 days.
4. Study drug dosing to occur 28 days from the previous dose with a window of -4 days to +3 days of the intended dosing day.
5. Full physical exam
6. Directed physical exam
7. Assess vital signs on Day 0 at Time 0 (pre-dose), within + 5 minutes after completion of infusion of the first component of study drug, and 1 hour (+ 5 minutes) after completion of infusion of the second component of study drug.
8. Height measured once during Screening only.
9. Screening labs to include: SUA, anti-PEG-antibodies, hepatitis B and C antibodies, human immunodeficiency virus 1/2 (HIV1/2), hemoglobin-A1c (HbA1c), glucose, triglycerides, LDL, glucose-6-phosphate dehydrogenase (G6PD), WBC, AST, ALT, Hgb, serum creatinine, and serum phosphate, urinalysis
10. Begin ULT washout at least 7 days prior to Day 0 of Treatment Period 1.
11. Begin colchicine 0.6 mg QD premedication at least 7 days prior to Day 0 of Treatment Period 1. Patients not already taking colchicine will receive colchicine 1.2 mg as a single loading dose followed by the 0.6 mg every day regimen. If the patient cannot tolerate the loading dose level of 1.2 mg, then the patient will initiate and maintain colchicine at 0.6 mg.
12. Pretreatment to minimize potential infusion reactions: oral steroids at 24 (\pm 12) hours and oral antihistamines at 12 (\pm 2) hours and 2 (\pm 1) hours and IV steroids at 1 (\pm 0.5) hours prior to study medication.
13. Chemistry labs to include: Alkaline phosphatase, alanine aminotransferase (ALT), aspartate aminotransferase (AST), total bilirubin, blood urea nitrogen (BUN), creatinine, fibrinogen, glucose (fasting), phosphorous, electrolytes (sodium, potassium, chloride, bi-carbonate, phosphate and magnesium).
14. Hematology labs to include: white blood cells (WBC) count with differential, red blood cell (RBC) count, hematocrit (Hct), hemoglobin (Hgb), mean corpuscular volume (MCV), mean corpuscular hemoglobin (MCH), mean corpuscular hemoglobin concentration (MCHC), red cell distribution width (RDW), platelet (Plt) count, mean platelet volume (MPV)
15. Coagulation labs to include: prothrombin time (PT), activated partial thromboplastin time (aPTT), international normalized ratio (INR)
16. Lipid labs to include: total cholesterol, HDL, LDL, triglycerides
17. Urinalysis to include: urinary protein, albumin, creatinine, pH, specific gravity, blood, glucose, ketones, bilirubin, leukocyte, esterase, WBC, RBC, crystals, casts (cast types), epithelial cells (renal and nonrenal), bacteria, mucus, and yeast.
18. Refer to [Section 11.3](#) for Health Questionnaires.
19. During Screening, SAE collection begins at time of signing informed consent. Non-serious AE will not be collected during Screening.
20. Visit window is -2 days to +6 days

Abbreviations: Ab: antibody; D (d): day; ECG: electrocardiogram; EOS: end of study; ET: early termination; h: hour; RCTC: Rheumatology Common Toxicity Criteria; Scr: Screening Period; SUA: serum uric acid; TP: treatment period; ULT: urate lowering therapy

APPENDIX B SCHEDULE OF ASSESSMENTS: SEL-212 DOSING AND SUA DURING THE TREATMENT PERIOD

Assessments Day Timepoint	Treatment Periods: 1, 2, 4, and 5				Treatment Periods 3 and 6								
	D0 ¹				D21	D0 ¹				D7	D14	D21	D28 ²
	0h	~1.5h	~3.5h	~4.5h		0h	~1.5h	~3.5	~4.5h				
Premedicate: Infusion Reaction	X ³					X							
Blood Sample: SUA	X ⁴			X ⁵	X	X ⁴				X ⁵	X	X	X
Study Drug Infusion (Component 1) ⁶	X----- ⁷					X----- ⁷							
Study Drug Infusion (Component 2) ⁸		X ⁷ -----X					X ⁷ -----X						

1. Study drug dosing to occur 28 days from the previous dose with a window of -4 days to +3 days of the intended dosing day.
2. Treatment Period 6 only.
3. Pretreatment to minimize potential infusion reactions: oral steroids at 24 (\pm 12) hours and oral antihistamines at 12 (\pm 2) hours and 2 (\pm 1) hours and IV steroids at 1 (\pm 0.5) hours prior to study medication.
4. Obtain sample prior to study drug infusion.
5. Obtain sample 1 (\pm 0.25) hour after completion of infusion of Component 2.
6. Component 1 will be SEL-110.36 for patients randomized to treatment with SEL-212.
7. Before starting infusion with Component 2, a period of up to 15 minutes is permitted after completion of infusion of Component 1.
8. Component 2 will be SEL-037 for patients randomized to treatment with SEL-212.

APPENDIX C SCHEDULE OF ASSESSMENTS FOR PATIENTS RANDOMIZED TO KRYSTEXXA

Assessment	Scr.		Treatment Period (TP)																EOS ¹	ET	
			TP1 ²		TP2 ²		TP3 ²				TP4 ²		TP5 ²		TP6 ²						
Day	-45 d	-7 d ³	D0	D14	D0 ⁴	D14	D0 ⁴	D7	D14	D21	D0 ⁴	D14	D0 ⁴	D14	D0 ⁴	D7	D14	D21	D28 ²⁰		
Informed Consent	X																				
Demographics	X																				
Inclusion/Exclusion	X																				
Medical History	X																				
Physical Examinations	X ⁵		X ⁶		X ⁶		X ⁶				X ⁶		X ⁶		X ⁶					X ⁵	X ⁵
Vital Signs	X	X	X ⁷	X ⁷	X ⁷	X ⁷	X ⁷	X ⁷			X ⁷	X ⁷	X ⁷	X ⁷	X ⁷	X ⁷	X	X	X	X	
Weight and Height ⁸	X	X		X		X			X			X		X			X		X	X	X
Tophus Assessment	X																			X	X
12-Lead ECG	X																			X	X
Screening Labs ⁹	X																				
Screening Lab: Anti-PEG-Ab	X																				
Urine Pregnancy Test	X																				
Washout: ULTs		X ¹⁰	Patients will abstain from ULT use after the ULT washout period																		
Document ULTs Discontinued		X																			
Dispense Premedication: Gout Flare and Infusion Reaction		X																			
Premedication: Gout Flare		X ¹¹	Continuously																		
Premedication: Infusion Reaction			X ¹²	X ¹²	X ¹²	X ¹²	X ¹²		X ¹²		X ¹²	X ¹²	X ¹²	X ¹²	X ¹²		X ¹²				
Safety Labs: Chemistry ¹³	X		X	X		X			X			X		X			X		X	X	X
Safety Labs: Hematology ¹⁴	X		X	X		X			X			X		X			X		X	X	X
Safety Labs: Coagulation ¹⁵	X		X	X		X			X			X		X			X		X	X	X
Safety Labs: Lipids ¹⁶	X		X	X		X			X			X		X			X		X	X	X
Safety Labs: Urinalysis ¹⁷	X		X	X		X			X			X		X			X		X	X	X
Safety Labs: Anti-drug-Ab																				X	X
Gout Flare Assessment	X		X	X	X	X	X	X	X	X	X	X	X	X	X	X	X	X	X	X	
Joint Assessment (tenderness, swelling)			X								X								X		X
Health Questionnaires ¹⁸			X								X								X		X

Appendix C, SCHEDULE OF ASSESSMENTS FOR PATIENTS RANDOMIZED TO KRYSTEXXA, CONTINUED

Assessment	Scr.	Treatment Period (TP)														EOS ¹	ET				
		TP1 ²		TP2 ²		TP3 ²				TP4 ²		TP5 ²		TP6 ²							
Day	-45 d	-7 d ³	D0	D14	D0 ⁴	D14	D0 ⁴	D7	D14	D21	D0 ⁴	D14	D0 ⁴	D14	D0 ⁴	D7	D14	D21	D28 ²⁰		
Collect Sample for SUA	X		Refer to Schedule of Assessments in Appendix D for SUA Sample Collection during Treatment Period																	X	
Study Drug Administration			Refer to Schedule of Assessments in Appendix D for Study Drug Administration during the Treatment Period																		
Concomitant Medications / Procedures			Continuously															X	X		
AE/SAE Collection	X ¹⁹	X ¹⁹	Continuously															X	X		

1. Phone call at 30 (+ 4) days after the last study drug infusion for assessment of concomitant medications/procedures, AEs, and SAEs.
2. Visit window at Day 14 of each Treatment Period is -2 days to +3 days; visit window at Day 7 and 21 of TP3 and TP6 is -2 days to +3 days.
3. Visit window is -2 days.
4. Study drug dosing to occur 14 days from the previous dose with a window of -2 days to +3 days of the intended dosing day.
5. Full physical exam
6. Directed physical exam
7. Assess vital signs on Day 0 and 14 at Time 0 (pre-dose), and 1 hour (+ 5 minutes) after completion of infusion.
8. Height measured once during Screening only.
9. Screening labs to include: SUA, anti-PEG-antibodies, hepatitis B and C antibodies, human immunodeficiency virus 1/2 (HIV1/2), hemoglobin-A1c (HbA1c), glucose, triglycerides, LDL, glucose-6-phosphate dehydrogenase (G6PD), WBC, AST, ALT, Hgb, serum creatinine, and serum phosphate
10. Begin ULT washout at least 7 days prior to Day 0 of Treatment Period 1.
11. Begin colchicine 0.6 mg QD premedication at least 7 days prior to Day 0 of Treatment Period 1. Patients not already taking colchicine will receive colchicine 1.2 mg as a single loading dose followed by the 0.6 mg every day regimen. If the patient cannot tolerate the loading dose level of 1.2 mg, then the patient will initiate and maintain colchicine at 0.6 mg.
12. Pretreatment to minimize potential infusion reactions: oral steroids at 24 (\pm 12) hours and oral antihistamines at 12 (\pm 2) hours and 2 (\pm 1) hours and IV steroids at 1 (\pm 0.5) hours prior to study medication.
13. Chemistry labs to include: Alkaline phosphatase, alanine aminotransferase (ALT), aspartate aminotransferase (AST), total bilirubin, blood urea nitrogen (BUN), creatinine, fibrinogen, glucose (fasting), phosphorous, electrolytes (sodium, potassium, chloride, bi-carbonate, phosphate and magnesium).
14. Hematology labs to include: white blood cells (WBC) count with differential, red blood cell (RBC) count, hematocrit (Hct), hemoglobin (Hgb), mean corpuscular volume (MCV), mean corpuscular hemoglobin (MCH), mean corpuscular hemoglobin concentration (MCHC), red cell distribution width (RDW), platelet (Plt) count, mean platelet volume (MPV)
15. Coagulation labs to include: prothrombin time (PT), activated partial thromboplastin time (aPTT), international normalized ratio (INR)
16. Lipid labs to include: total cholesterol, HDL, LDL, triglycerides
17. Urinalysis to include: urinary protein, albumin, creatinine, pH, specific gravity, blood, glucose, ketones, bilirubin, leukocyte, esterase, WBC, RBC, crystals, casts (cast types), epithelial cells (renal and nonrenal), bacteria, mucus, and yeast.
18. Refer to [Section 11.3](#) for Health Questionnaires.
19. During Screening, SAE collection begins at time of signing informed consent. Non-serious AE will not be collected during Screening.
20. Visit window is -2 days to +6 days

Abbreviations: Ab: antibody; D (d): day; ECG: electrocardiogram; EOS: end of study; ET: early termination; h: hour; RCTC: Rheumatology Common Toxicity Criteria; Scr: Screening Period; SUA: serum uric acid; TP: treatment period; ULT: urate lowering therapy

APPENDIX D SCHEDULE OF ASSESSMENTS: KRYSTEXXA DOSING AND SUA DURING THE TREATMENT PERIOD

Assessments	Day Timepoint	Treatment Periods: 1, 2, 4, and 5						Treatment Periods 3 and 6								
		D0 ¹			D14			D0 ¹			D7	D14			D21	D28 ²
		0h	~2.0h	~3.0h	0h	~2.0h	~3.0h	0h	~2.0h	~3.0h		0h	~2.0h	~3.0h		
Premedicate: Infusion Reaction		X ³			X ³			X				X ³				
Blood Sample: SUA		X ⁴		X ⁵	X ⁴		X ⁵	X ⁴		X ⁵	X	X ⁴		X ⁵	X	X
Study Drug Infusion		X ----- X		X ----- X		X ----- X				X ----- X		X ----- X				

1. Study drug dosing to occur 14 days from the previous dose with a window of -2 days to +3 days of the intended dosing day.
2. Treatment Period 6 only.
3. Pretreatment to minimize potential infusion reactions: oral steroids at 24 (\pm 12) hours and oral antihistamines at 12 (\pm 2) hours and 2 (\pm 1) hours and IV steroids at 1 (\pm 0.5) hours prior to study medication.
4. Obtain sample prior to study drug infusion.
5. Obtain sample 1 (\pm 0.25) hour after completion of infusion.

Revision History

Version	Reason for Change	Date
1.1	
Clarifications, administrative corrections	12 APR 2019
2.0	
Clarifications, administrative correctionsUpdated study personnel informationReduced Screening threshold SUA to 7 mg/dL to allow for enrollment of all patients with serum uric acid above the limit of solubility	14 MAY 2019
2.1	
Clarifications, administrative correctionsUpdated study personnel informationAdded oral steroid premedication 24hr prior to dose	03 FEB 2020
3.0	
Clarifications, administrative correctionsUpdated study personnel information and sponsor addressUpdated secondary endpointsUpdated statistical analysis population definitionsUpdated primary efficacy population to be ITTUpdated statistical analysis approach for gout flare endpointClarification of visit windows	08 JUN 2020

SAP	Statistical Analysis Plan
Scr	Screening Period
SF-36	Short Form Health Survey 36
SUA	Serum Uric Acid
SOC	System Organ Class
SS	Safety Set
TEAE	Treatment-emergent adverse events
TLFs	Tables, Listings and Figures
TP	Treatment Period
ULN	Upper limit of normal
ULT	Uric acid lowering therapy
WHO-DD	World Health Organization Drug Dictionary
WBC	White Blood Cell

This document is confidential.

2. Purpose

The purpose of this statistical analysis plan (SAP) is to ensure that the data listings, summary tables and figures which will be produced, and the statistical methodologies that will be used, are complete and appropriate to allow valid conclusions regarding the study objectives.

2.1. Responsibilities

Syneos Health will perform the statistical analyses and are responsible for the production and quality control of all tables, figures and listings.

2.2. Timings of Analyses

The primary analysis of safety and efficacy is planned after all patients complete the final study visit or terminate early from the study.

An interim analysis will be conducted when 100% of patients are scheduled to have completed 3 months of study treatment (ie. scheduled to have completed Treatment Period (TP) 4 Day 0 visit). Since this is an open label study, unblinding of Syneos personnel is not applicable when performing interim analyses. Selecta is blinded to all post dose serum uric acid (SUA) values and the primary endpoint throughout the study except that Selecta will be unblinded to the primary endpoint results at delivery of the interim analysis. As such, the interim analysis will be performed so that the study data will be collected once the timepoint criteria above is met, but the study data will be held by Syneos as a mitigation against significant COVID-19 pandemic disruption in the dataset. The primary and secondary endpoints will not be calculated nor the interim analysis results delivered to Selecta until requested by Selecta due to significant disruption in the study or due to the last patient dosing having occurred in the study. Selecta will remain blinded to individual subject SUA data until the final analysis. Syneos's biostats and programming study team will prepare all report summaries for the interim analyses. The purpose of the interim analysis is for business planning and so a protocol update including sample size adjustment is not applicable.

This document is confidential.

3. Study Objectives

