7.5 Criteria for Study Termination

The study can be terminated at any time at the Sponsor's sole discretion. Otherwise, the study will be terminated when all patients have completed follow-up assessments ([Section 20](#)) or the Sponsor or regulatory agency(ies) have determined there is an unacceptable risk to patients or additional dosing or procedures are not warranted or necessary.

The study may be terminated at a particular investigational site under the following conditions:

- The Investigator fails to enroll patients at an acceptable rate;
- The Investigator fails to comply with pertinent regulations;
- There is insufficient adherence (i.e., compliance) to the protocol;
- Knowingly false information is submitted to the IRB, Sponsor or designee, or regulatory authorities.

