13.1 Sample Size Determination

The primary efficacy criterion in this study is defined as the percentage of subjects who achieve and maintain reduction of SUA < 6 mg/dL for at least 80% of the time during Treatment Period 3 and Treatment Period 6.

The percentage of responders according to the above criterion is assumed to be 65% in the SEL-212 arm and 44% in the KRYSTEXXA arm.

Using the Chi-square test for comparison between the SEL-212 arm and the KRYSTEXXA arm, and considering a one-sided alpha=5% and the statistical power of 80%, results in 69 subjects per treatment group. Taking into account that some subjects may be excluded from the modified Intent-to-Treat (mITT) analyses (Section 13.2.4), 75 subjects per treatment group will be randomized. For the sample size estimation, Chi-square test, instead of the Cochran-Mantel-Haenszel test, is used although the randomization will be stratified for tophus presence (yes/no) as there is no valid assumption of the distribution of this stratification variable within the eligible subject population.

Sample size calculations were performed with the software package nQuery Advisor® Sample Size Calculator V. 8.2.1.0.

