5.6. Protocol Deviations

All protocol deviations related to study inclusion or exclusion criteria, conduct of the trial, patient management, dosing, and sampling procedures or patient assessment will be listed. The list of protocol deviations will be reviewed by the Sponsor, the principal investigator, the study statistician and the study pharmacokineticist and finalized before database lock. Determination of whether the deviation is major or minor, or has impacts on primary efficacy assessment will be based on the biasing impact of the deviation on the safety and efficacy data. Major protocol deviations affecting the primary efficacy assessments include: 1) major protocol deviations that lead to premature study drug discontinuation; 2) major protocol deviations that lead to patients receiving study drug treatment in treatment periods 3 or 6 that they would not otherwise have received (such as incorrect application of the protocol stopping rules that allow a patient to continue dosing despite having met the stopping criteria); and 3) protocol deviations that involve out of window sampling of SUA due to a) visits occurring outside of the protocol visit window for dosing days (where dosing days refer to dosing visits of patients still on study drug who have not previously been withdrawn from study drug) in Treatment period 3 and 6, b) visits occurring outside of the protocol visit

This document is confidential.

window for visits within TP3 or TP6 scheduled 1 week prior to the dosing days, c) visits occurring outside of the protocol visit window for TP6 D21 for patients who have not been withdrawn from study drug and for dosing day TP4D0, or d) visits occurring 35 days or more beyond TP6D0 for the TP6D28 visit for patients who have not been withdrawn from study drug, where the protocol visit window above refers to the current protocol window allowed at the time of analysis. Major protocol deviations affecting the primary efficacy assessments will be reviewed and determined periodically during clinical and medical review of protocol deviations during the study.

Protocol deviations related to Covid-19 will be identified and flagged.

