The estimator for the comparison between the treatment groups is defined as the difference in the proportion of responders between patients receiving SEL-212 versus those receiving KRYSTEXXA® during Treatment Periods 3 and 6. The statistical testing will be performed confirmatory using the Cochran-Mantel-Haenszel (CMH) test – considering the randomization stratum of tophus presence (yes/no) – with a one-sided type 1 error rate $\alpha = 5\%$. In addition, 90% two-sided confidence intervals for the overall treatment difference between SEL-212 and KRYSTEXXA® treatment groups without stratification will be computed. The analysis of the estimands will be carried out based on the ITT primarily. Supportive analyses will be performed on the mITT and the PP.

A logistic regression model to compare treatment difference controlling for presence of tophus will be performed as supportive analysis.

In addition, a sensitivity analysis will be performed as below for the primary endpoint:

- If a subject withdraws from study treatment before completing period 6 due to stopping rules met for treatment, the subject will be considered as a non-responder for the primary efficacy endpoint.
- If a subject withdraws from the study before completing period 6 or the study terminates prior to a subject completing period 6, the primary efficacy endpoint is based on SUA assessment for period 3 where $T1$ be the total time interval in hours for Treatment Period 3 of which $W1$ hours is the time interval during which SUA level is < 6 mg/dL:

$$\text{Percentage (p)} = \frac{W1}{T1} \times 100$$

Summary tables of the percentage of responders (patients who achieve and maintain reduction of SUA < 6 mg/dL for at least 80% of the time) will be provided by treatment group. Additionally, a summary table with the total time a patient has SUA values < 6 mg/dL will be provided for treatment period 3 and treatment period 6 by treatment group.

Summary tables of the actual values and change from baseline for SUA results will be provided for each scheduled sampling time point by treatment group.

This document is confidential.

Additionally, mean SUA level, reduction in mean SUA and percent reduction in mean SUA from baseline during Treatment Periods 3 and 6, during Treatment 3, and during Treatment Period 6 will be summarized by treatment group respectively and will be compared for treatment difference using ANOVA model with presence of tophus and treatment group as fixed factors

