7.4. Deviation from Analyses Planned in Protocol

7.4.1. Additional analyses

The following analyses are added even though they are not included in the protocol:

- Interim analysis.
- Subgroup analyses on the secondary endpoint by patient's primary efficacy endpoint (responder vs. non-responder).

The following analyses have been added as a result of the impact of Covid-19 on the study which may result in a larger anticipated number of subjects not completing the study and therefore not undergoing the assessments required for the primary efficacy endpoint or the study being stopped prematurely by sponsor decision. This is in line with FDA Guidance on Conduct of Clinical Trials of Medical Products during COVID-19 Pandemic Guidance for Industry, Investigators, and Institutional Review Boards.

- Additional analyses suggested to primary endpoint as sensitivity analyses to determine if the impact that these have on the conclusions of the study and to describe the impact of Covid-19 on the study performance.
- A sensitivity analysis which limited the analysis to results processed in the central laboratory to determine if this resulted in different conclusions to those found from the full analysis to determine consistency in laboratory testing between central and local laboratories.
- Kaplan-Meier analysis of withdrawal from study by treatment arm and presence of tophus to determine if subjects withdraw from the study in different proportions and at different rates within the treatment groups and depending on the presence of tophus.
- Kaplan-Meier analysis of withdrawal from study due to an adverse event by treatment arm and presence of tophus to determine if subjects experience adverse events in different proportions and at different rates within the treatment groups and depending on the presence of tophus.
- Poisson regression with number of gout flares experienced during treatment periods 1-6 as the dependent variable, treatment and the presence of tophus as independent variables and length of follow up as a covariate. The ITT population would be used to conduct this analysis. Similar analysis is done for periods 4-6.

This document is confidential.

8. Safety

The population used for safety analyses will be the Safety Set (SS). Safety will be assessed on the basis of adverse event (AE), clinical laboratory data, ECG parameters, physical examinations, and vital signs.

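### The sponsor can see the comparative primary result before the per-protocol set is closed, and the plan does not bar a success claim after a result-driven stop

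*SAP*

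**What the plan says.** **Interim.** SAP 2.2 adds an interim analysis that SAP 7.4.1 acknowledges is not in the protocol. Data are cut when every patient is scheduled to have reached TP4 Day 0. The endpoints are neither calculated nor delivered "until requested by Selecta due to significant disruption in the study or due to the last patient dosing having occurred in the study". At that point "Selecta will be unblinded to the primary endpoint results at delivery of the interim analysis", while individual SUA values stay masked to the sponsor until the final analysis. The stated purpose is business planning, without a sample size change. SAP 9 repeats the timing and gives no boundary or alpha split.

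**Stopping.** Protocol 7.5: "The study can be terminated at any time at the Sponsor's sole discretion". SAP 7.4.1 foresees "the study being stopped prematurely by sponsor decision" as a possible effect of COVID-19.

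**Scoring after a stop.** The primary rule in SAP 7.1 makes a subject who withdraws before completing TP6, or who returns to urate-lowering therapy, a non-responder. Only the sensitivity analysis in the same section covers the case where "the study terminates prior to a subject completing period 6". It scores that patient on TP3 alone.

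**PP set.** SAP 5.6: "The list of protocol deviations will be reviewed by the Sponsor, the principal investigator, the study statistician" and the pharmacokineticist, and it is final only before database lock. ITT is primary and PP supportive for the primary endpoint (SAP 7.1). The SUA responder secondaries are analysed on ITT and PP (SAP 7.2.1).

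**The concern.** Two things are left open after the comparative result is known.

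The first is PP membership. Whether a deviation is major rests partly on its judged biasing impact, and the visit windows applied are those in force at the time of analysis. A reviewer who has seen the result can tell which way an exclusion would move it.

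The second is the status of a stop. The business-planning label rules out a sample size change. It does not rule out ending the study on a favourable result and claiming success. If that were done, the trial would have had two chances at one-sided 5%. The scoring of patients without TP6 could also be argued afterwards, because the primary analysis is silent on a sponsor stop.

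**Working it through.** **1. The plan's own figure.** Inputs (Protocol 13.1): rates "assumed to be 65% in the SEL-212 arm and 44% in the KRYSTEXXA arm"; "considering a one-sided alpha=5% and the statistical power of 80%, results in 69 subjects per treatment group". With pooled variance and mean rate (0.65 + 0.44)/2 = 0.545:

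n = [1.645 × √(2 × 0.545 × 0.455) + 0.842 × √(0.65 × 0.35 + 0.44 × 0.56)]² / 0.21² = (1.158 + 0.579)² / 0.0441 ≈ 68.5, so 69. The stated size reproduces. Power is 80.3% at 69 per arm and 83.1% at the 75 to be randomised.

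**2. Timing.** Treatment lasts 168 days, and the last scheduled infusion is on Day 140 (SEL-212) or Day 154 (KRYSTEXXA) (Protocol 7.1). If last dosing means the last infusion in the study, a last-dosed patient on schedule is 168 − 140 = 28 or 168 − 154 = 14 days from TP6 Day 28. Delivery can therefore precede the final data under either trigger, but little is outstanding under this one.

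**3. Error rate if success could be claimed at either look.** The documents give no information fraction and no correlation between looks, so both are assumed. The simulation used 200,000 runs with 75 per arm and equal arms. All patients are scored on TP3 at the interim. Final responders are the TP3 responders who are kept, with a final rate of 44%, so the TP3 rate is 0.44/(1 − loss). Success is pooled z > 1.645.

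| TP3 responders lost by TP6 | TP3 rate | Correlation of looks | Final test only | Either look |
|---|---|---|---|---|
| 0% | 44.0% | 1.00 | 5.2% | 5.2% |
| 5% | 46.3% | 0.95 | 5.2% | 6.2% |
| 10% | 48.9% | 0.91 | 5.1% | 6.6% |
| 20% | 55.0% | 0.80 | 5.1% | 7.7% |
| 30% | 62.9% | 0.68 | 5.2% | 8.6% |

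The final-only column slightly exceeds 5% because counts are discrete. As a check, the bivariate normal formula 1 − P(Z1 < 1.645, Z2 < 1.645) gives 6.3%, 6.8%, 7.5% and 8.0% at correlations 0.95, 0.90, 0.80 and 0.70.

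**4. Error rate if the look leads only to stopping on a poor result.** P(Z1 > 0, Z2 > 1.645) is 4.9% at correlation 0.71 and 5.0% at 0.90. There is no inflation.

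**5. Sensitivity of PP to a few exclusions.** The counts are hypothetical, and an unstratified pooled z-test stands in for the CMH test. With 42/75 against 33/75, z = 0.12/0.0816 = 1.47 and one-sided p = 0.071. Excluding two SEL-212 non-responders gives 42/73 against 33/75, z = 0.1353/0.0822 = 1.65 and p = 0.0498. Excluding three gives p = 0.041. The ITT result stays at 0.071 throughout.

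**6. Cost of an alpha split.** With O'Brien-Fleming-type spending at assumed fractions 0.5, 0.75 and 0.90:

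| Fraction | Interim level | Final level | Power of final test alone, 75 per arm |
|---|---|---|---|
| 0.50 | 0.0056 | 0.0482 | 82.7% |
| 0.75 | 0.0236 | 0.0431 | 81.2% |
| 0.90 | 0.0388 | 0.0397 | 80.1% |

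A fixed interim level of 0.001 leaves the final level at 0.0498 to 0.050 and power at 83.1%.

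**The case against.** **On the error rate.** A reader might infer that the interim already costs the trial its 5% level. The documents do not support that. SAP 2.2 places the primary analysis after all patients finish or leave, SAP 7.1 describes a single confirmatory CMH test, and the interim has no success criterion. Inflation needs a stop followed by a claim, which the plan neither schedules nor forbids. TP3 is due for everyone at the data cut, so the looks are probably highly correlated. Protocol 7.6.3.2 reports that all evaluable Part C patients controlled at Week 12 were also controlled at Week 24. That is SEL-212 only, but for that arm it points to the low end of the range. All of this stands.

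**On the TP3-only rule.** It is also tempting to read it as a ready-made primary endpoint for a stopped trial. SAP 7.1 labels it a sensitivity analysis. What remains is that the primary rule says nothing about a sponsor stop.

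**On PP.** Several safeguards count. Individual SUA stays masked; SAP 5.6 lists the relevant deviation categories and has them determined periodically; SAP 5.5 exempts patients who leave after meeting a stopping rule from the visit-completion requirement; and ITT is primary, so the main result does not turn on PP. They limit the problem without closing it. Sponsor personnel know the treatment assignments (Protocol 7.6.1), and a withdrawal under the SUA stopping rules signals a high SUA. Calling a deviation major still involves judgement, and periodic review is not tied to interim delivery.

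**On the remedy.** Forbidding every superiority claim after any stop would go too far. It would also catch a safety or regulatory stop, where nothing was selected on efficacy.

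**Conclusion.** The concern holds in a limited form. As written, the plan lets PP membership be settled by people who know the comparative result. This affects the supportive analysis of the primary endpoint and one of the two sets used for the SUA responder secondaries. In a borderline case two exclusions are enough to cross 5%, on assumed counts.

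The 5% level is not breached by the look. It lacks an explicit safeguard against a result-driven stop that is then claimed as a success. In that event the one-sided error would be about 5% to 8.6%, for an assumed loss of 0% to 30% of TP3 responders by TP6. The simulation takes TP3-only scoring at the interim and nests final responders within TP3 responders, which simplifies the time-weighted endpoint. The exposure lies mainly with the undefined disruption trigger.

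The silence on scoring a sponsor stop in the primary analysis is a separate gap. Together these make a cheap improvement worth having, not a flaw that invalidates the design.

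**What to change.** Amend SAP 2.2, 5.6, 7.1 and 9:

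1. **PP set.** Finalise and sign the deviation classification and PP membership for all data in the cut before the interim endpoints are calculated. Have later deviations classified by those existing reviewers who have not seen the interim results.
2. **Status of the interim.** State that it is not a test and cannot support an efficacy claim, and that the confirmatory CMH test is run once on final data. Alternatively, pre-specify an alpha split, which 75 per arm absorbs at about 80% power or more under the planning assumptions.
3. **Stopping.** Define the disruption trigger. Document any decision to stop for disruption before the interim endpoints are calculated. State how patients cut off by a sponsor stop are scored in the primary analysis.

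The cost is wording and one extra sign-off before delivery. The no-claim statement costs no power. The sponsor gives up the option of using the interim result to choose an early stop while keeping an unadjusted confirmatory claim.
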